### **Trial Objective and Purpose:**

The purpose of this trial is to determine if the upstream use of metformin in patients with atrial fibrillation and obesity undergoing a rhythm control strategy will increase the frequency of maintenance of sinus rhythm at six months. The primary endpoint is the number of patients in normal sinus rhythm after six months of follow up. Secondary endpoints are amount of weight loss, change in BMI, change in hemoglobin A1c, number of thromboembolic events, and burden of atrial fibrillation based on the Atrial Fibrillation Severity Score (AFSS).

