#### **Trial Design:**

The proposed study will be a randomized control trial comparing metformin therapy to a control group in patients with a BMI  $\geq$ 27 and atrial fibrillation who have elected to undergo a rhythm control strategy with ablation. Upstream therapy with Metformin will be used in a randomized fashion. The only variation to the standard of care will be the addition of Metformin therapy and additional blood draws for safety monitoring and EKGs for measuring outcomes in both the intervention and control groups.

Patients meeting the below inclusion and exclusion criteria who provide informed consent will be randomized to control versus metformin therapy six weeks prior to rhythm control.

At baseline all study patients will be assessed for:

Age, Gender, Weight, BMI, Tobacco Use, Hypertension, Hemoglobin A1c, Hyperlipidemia, serum CRP, glomerular filtration rate estimating equation (eGFR), B12, liver function tests (AST, ALT, ALP, bilirubin, albumin, INR), lactic acid, History of Coronary Artery Disease by MI, PCI, or CABG, History of Valvular Disease, History of Obstructive Sleep Apnea, Type of AF and duration, Number of Antiarrhythmic Medications (not including beta-blockers or calcium channel blockers).

In addition, patients will fill out a survey to determine their Atrial Fibrillation Severity Score (AFSS) - a validated tool to assess the symptomatic burden of AF - and will receive education on dietary changes and exercise

Metformin will be initiated at 500 mg daily and increased as tolerated to 2000 mg daily over a three week period. Subjects will be instructed to hold Metformin on the day of any procedure or study requiring the administration of intravenous contrast and to resume 48 hours after the contrast administration and reinstituted only after renal function has been reevaluated and found to be at the patient's baseline. All patients will receive information on dietary changes to promote weight loss and will be encouraged to increase exercise activities. Patients will discontinue treatment at any time they are found to meet the baseline exclusion criteria for the study.

The initiation of the drug and the dosage increases will be overseen by a designee (mid-level cardiology practitioner) who will be responsible for stopping dosage increases if side effects occur. Six weeks after the initiation of drug the patient will undergo ablation with the intent of achieving rhythm control.

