#### **Outcomes and Assessment of Efficacy:**

The primary outcome by intention to treat analysis will be maintenance of sinus rhythm by chart review, EKG, and Atrial Fibrillation Severity Score at 3 and 6 months after the initial attempt at rhythm control.

Secondary outcomes will include hospitalization related to arrhythmic events or medication side effects, number of antiarrhythmic medications, number of repeat ablations, BMI, Hemoglobin A1c, and number of thromboembolic events.

Pre-specified subgroup comparisons will include comparing patients randomized to metformin who have a 5% reduction in weight at 6 months to all control patients who achieve a 5% reduction in weight, and to all control patients.

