#### **Statistics:**

We expect a 30% recurrence of AF after patients undergo ablation. After ablation, we expect the recurrence of AF to be 30% less in the intervention group of patients on metformin than the control group.

Using an 80% power at a 95% confidence interval, the sample size of the control group (ablation only) and the intervention group (ablation plus metformin) will be 400 each for a two tailed study, accounting for up to a 3% attrition rate in each group. The total sample size of this study will be 800. It is estimated to take five years to accrue subjects.

Statistical methods employed to analyze outcomes will be a Pearson's  $X^2$  test for categorical variables. Analysis of Variance will be used for continuous variables. All tests are two-sided and P < .05 will be used to indicate a statistically significant difference.

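### The protocol states two inconsistent primary endpoints, six-month rhythm status and maintenance at 3 and 6 months, with no rule for combining visits or sources

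*Combined protocol and SAP*

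**What the plan says.** Two sections of the combined protocol and SAP define the primary endpoint, and both are current text.

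- **Trial Objective and Purpose.** The purpose is to learn whether metformin "will increase the frequency of maintenance of sinus rhythm at six months". The next sentence gives the endpoint: "The primary endpoint is the number of patients in normal sinus rhythm after six months of follow up". AF burden by AFSS is in the list of secondary endpoints.
- **Outcomes and Assessment of Efficacy.** The primary outcome, by intention to treat, is "maintenance of sinus rhythm by chart review, EKG, and Atrial Fibrillation Severity Score at 3 and 6 months after the initial attempt" (that is, the first ablation). Among the secondary outcomes are "number of antiarrhythmic medications, number of repeat ablations".

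Three other places bear on the point.

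- **Trial Design** schedules an EKG at the first rhythm-control attempt and at the 3-month and 6-month visits. It allows extra visits at the treating physician's discretion and leaves other care alone: "The only variation to the standard of care will be the addition of Metformin therapy".
- **Statistics** gives the planning rate for control as "We expect a 30% recurrence of AF after patients undergo ablation". The rate on metformin follows from a second statement: "we expect the recurrence of AF to be 30% less in the intervention group of patients on metformin than the control group". Neither rate has a time point.
- **Statistics** also sets 400 per arm, 80% power, a two-sided 5% level, up to 3% attrition and a Pearson chi-square test.

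**The concern.** The two definitions differ in time (month 6 alone, or months 3 and 6), in concept (status, or maintenance) and in measurement (AFSS secondary, or part of the primary). Nothing in the documents says which one governs.

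The patients affected are those who return to AF and are then restored to sinus rhythm. The protocol expects such patients, because it counts repeat ablations and antiarrhythmic drugs as secondary outcomes, but it does not say whether rescue counts as failure. Two analysts following the plan faithfully could therefore report different primary results, and the choice could be made with the data in view. The planning rates cannot be checked against the endpoint either, because it is not known which endpoint they describe.

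**Working it through.** **1. One patient under each text.** Take a patient in AF on the 3-month EKG, then re-ablated, and in sinus rhythm on the 6-month EKG.

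| Text and reading | Month 3 | Month 6 | Primary result |
|---|---|---|---|
| Trial Objective and Purpose: status after six months | not used | sinus rhythm | success |
| Outcomes: sinus rhythm required at both visits | AF | sinus rhythm | failure |
| Outcomes: two separate assessments | AF | sinus rhythm | failure at month 3, success at month 6 |

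The third row avoids a flat clash at month 6, but leaves two primary results and no rule for combining them. On any reading, the AFSS enters the primary outcome in one section and is secondary in the other, with no failing score.

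**2. The plan's own sample size.** Inputs from Statistics: control 30%; metformin 0.30 × (1 − 0.30) = 21%; two-sided 5% (z = 1.96); 80% power (z = 0.84); 3% attrition.

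- n = [1.96·√(2p̄(1−p̄)) + 0.84·√(p₁(1−p₁) + p₂(1−p₂))]² / (p₁−p₂)², with p̄ = 0.255, gives 367 per arm.
- With continuity correction, n′ = (n/4)·[1 + √(1 + 4/(n·|p₁−p₂|))]² gives 389, and 389/0.97 = 401.03, rounded up to 402.

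This reproduces the stated 400 within rounding. Without the correction the result is 367/0.97, or 379. The sample size is not in dispute.

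**3. Power at the evaluable number.** 400 × 0.97 = 388 per arm. The planned test is Pearson's, so no continuity correction is used:

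Power = Φ{ [|p₁−p₂|·√388 − 1.96·√(2p̄(1−p̄))] / √(p₁(1−p₁) + p₂(1−p₂)) }

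For 30% v 21%: (0.09 × 19.70 − 1.96 × 0.6164) / 0.6131 = 0.921, so power is 82%.

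**4. How much the definition could matter.** Let r be the share of failures back in sinus rhythm at month 6, equal in both arms. The documents give no value for r, so every value is an assumption.

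*Case A: 30% v 21% counts failure regardless of rescue, and six-month status is analysed.* Failure rates become 30%·(1−r) and 21%·(1−r).

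| r | Control v metformin | Power |
|---|---|---|
| 0 | 30.0% v 21.0% | 82% |
| 10% | 27.0% v 18.9% | 77% |
| 20% | 24.0% v 16.8% | 70% |

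At r = 20%, the patients scored differently by the two definitions number 388 × 0.30 × 0.20 = 23.3 in control and 388 × 0.21 × 0.20 = 16.3 on metformin.

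*Case B: 30% v 21% is already six-month status.* Analysing status keeps power at 82%. Scoring failure regardless of rescue gives rates of 30%/(1−r) and 21%/(1−r): 33.3% v 23.3% and 87% power at r = 10%, or 37.5% v 26.3% and 92% at r = 20%. No power is lost.

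**The case against.** The best defence is that the two sections mean the same thing. The 3-month and 6-month time points in Outcomes match the visit schedule, so that section may simply list when rhythm is assessed, and its month-6 assessment then agrees with the stated endpoint. Trial Objective and Purpose itself moves from maintenance to status in consecutive sentences, apparently without intending a difference. This has force. A reader might infer that the example patient is simply a failure under Outcomes; that holds on only one of the two readings. The defence does not remove the inconsistency, because separate assessments still leave two primary results and the AFSS mismatch remains.

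A second objection is that the size is hypothetical. That also stands. Power falls in one case and is kept or raised in the other, and no rescue rate is documented. Rescue is not the only source of a gap either: AF that ends by itself before the 6-month EKG also separates the definitions, and the inclusion criteria do not restrict AF type.

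A reader might go further and infer bias or an inflated false-positive rate from unequal rescue, since no placebo or masking is described. Unequal rescue cannot be excluded, but nothing in the documents supports a particular imbalance, so no figure for it belongs here.

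**Conclusion.** The inconsistency is real and should be fixed before analysis. It is more than missing detail: two current sections give different primary endpoints, no section reconciles them, and following the plan as written permits more than one primary result. That conclusion needs no assumption about rescue.

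The effect on power is only an illustration. It depends on an assumed rescue share, equal in both arms, and on what 30% means: from about 82% to 77% or 70% in case A at 10% or 20% rescue, and no loss in case B. A reader might conclude that the trial is underpowered or that 400 per arm is wrong. The documents do not support that, because the stated size reproduces from the stated rates. What cannot be confirmed is that those rates belong to the endpoint that will be analysed. The use of recurrence and maintenance leans towards counting rescued patients as failures, but without a time horizon it does not decide the point.

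**What to change.** State one binary primary endpoint, in identical terms, in Trial Objective and Purpose and in Outcomes and Assessment of Efficacy.

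- **Suggested definition.** Success is sinus rhythm on both the 3-month and the 6-month scheduled EKG. AF on either is failure, even if rhythm is later restored by repeat ablation, cardioversion or drug. This fits the time points in Outcomes and uses only assessments scheduled in both arms. Counting any charted AF as primary failure would be more exposed to unequal detection, because extra visits are discretionary and no masking is described.
- **AFSS.** Keep it as a secondary endpoint.
- **Supportive analyses.** Report any AF documented by chart review, and six-month EKG status regardless of rescue.
- **Alternative.** Six-month EKG status as primary is also acceptable, provided Outcomes is changed to match.
- **Statistics.** State the time point and definition to which 30% and 21% apply. Confirm or re-derive the rates, and restate the power if they do not fit the chosen endpoint. They should not simply be relabelled.

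The cost is wording in three sections and a check of the planning rates; the EKGs are already scheduled and chart review is already named. The downsides are that scheduled EKGs miss AF between visits and that the reported success rate may shift slightly. In case A, for example, control success would read 70% rather than 73% or 76% at 10% or 20% rescue.

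### Two sections give different secondary-endpoint lists and two roles for the AFSS, and separately every test is called significant at P < .05 with no order or adjustment

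*Combined protocol and SAP*

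**What the plan says.** Trial Objective and Purpose sets the primary endpoint as the count of patients in sinus rhythm at six months, then states: "Secondary endpoints are amount of weight loss, change in BMI, change in hemoglobin A1c, number of thromboembolic events, and burden of atrial fibrillation", the burden being scored by the AFSS. That is five secondary endpoints.

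Outcomes and Assessment of Efficacy states: "Secondary outcomes will include hospitalization related to arrhythmic events or medication side effects". It goes on to name counts of antiarrhythmic drugs and of repeat ablations, then BMI, HbA1c and thromboembolic events. That is six. The same section judges the primary outcome from three sources (chart, EKG and AFSS) at both 3 and 6 months.

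The Statistics section gives a Pearson chi-square test for categorical outcomes and analysis of variance for continuous ones. It adds: "All tests are two-sided and P < .05 will be used to indicate a statistically significant difference". It names no secondary endpoint, testing order or multiplicity adjustment, and it does not label secondary results as exploratory.

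Trial Design describes the AFSS as a survey of symptom burden that patients fill in. It describes added metformin as the treatment difference between arms. No placebo for the control arm and no blinding are described.

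**The concern.** A plan should let a reader say, before any data are seen, which outcomes are secondary. Here the answer depends on the section read. The stakes are moderate. Three of the outcomes found in only one list (hospitalization, antiarrhythmic drug count, repeat ablation) depend partly on clinicians' decisions, and the AFSS depends on patients' own reports. With no blinding described, a fixed list matters more than usual.

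The AFSS has a further problem. If a symptom score helps decide whether a patient counts as being in sinus rhythm, and no rule says how it combines with EKG and chart, two people could classify the same patient differently. The primary then rests partly on a self-report that knowledge of the assigned arm could affect.

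The significance rule is a separate matter. Applied to every secondary outcome alike, it allows a chance result on any one of them to be called significant.

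**Working it through.** **The plan's own figure.** The plan states no error rate for the secondary endpoints as a set. Its only calculated figure is the primary sample size of 400 per arm. Inputs from the Statistics section: 30% recurrence in controls, 30% fewer on metformin (0.30 × 0.70 = 0.21), 80% power, two-sided 5%, 3% attrition. The two-proportion formula gives 367 per arm, or 389 with a continuity correction. Then 389 / 0.97 = 401.03, rounded up to 402, within 3% of the stated 400. That figure is sound and this point does not affect it.

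**The two lists side by side.**

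| Outcome | Trial Objective and Purpose | Outcomes and Assessment of Efficacy |
|---|---|---|
| BMI | secondary, as change | secondary, form not stated |
| HbA1c | secondary, as change | secondary, form not stated |
| Thromboembolic events | secondary | secondary |
| Weight loss | secondary | not listed |
| AFSS | secondary, as AF burden | part of the primary |
| Hospitalization (arrhythmia or drug side effects) | not listed | secondary |
| Antiarrhythmic drug count | not listed | secondary |
| Repeat ablations | not listed | secondary |

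Distinct outcomes: 5 + 6 − 3 = 8. In one list only: 8 − 3 = 5. Neither list gives a time point.

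**Chance of at least one false positive.** Assume every null is true and each of k outcomes is tested once at 0.05. Under independence the chance is 1 − 0.95^k:

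- k = 5: 1 − 0.7738 = 22.6%
- k = 6: 1 − 0.7351 = 26.5%
- k = 8: 1 − 0.6634 = 33.7%

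The outcomes are not independent, and the documents give no correlations. As an assumed range, 400,000 simulated sets of two-sided z-tests with one common correlation give:

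| Assumed correlation | 5 outcomes | 6 outcomes | 8 outcomes |
|---|---|---|---|
| 0.3 | 21.0% | 24.0% | 30.0% |
| 0.5 | 18.3% | 20.8% | 25.0% |
| 0.8 | 12.8% | 13.9% | 15.7% |

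**Sensitivity to the count.** Treating weight and BMI as one measure gives k = 7 and 30.2%. Splitting hospitalization by cause gives k = 9 and 37.0%. Testing all eight at both 3 and 6 months gives k = 16 and 56.0%. These three assume independence, and the last is high because repeated readings in the same patients are correlated.

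**The case against.** The best defense is that the lists do not exclude each other. The second says its outcomes are included, which is not exhaustive wording, so the two can be read as one set of eight. That is fair, and the fix adopts that set. But the plan does not say so, and the reading does not settle the AFSS, which the second section places in the primary.

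Several stronger readings are tempting, and the documents do not support them:

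- **That the mismatch causes the 33.7%.** It does not. Each list alone gives 22.6% or 26.5%, and a single consistent list of eight would still give 33.7%. The mismatch accounts for about 7 to 11 percentage points under independence; the rest comes from unadjusted testing, which is common for secondary outcomes.
- **That one third is the expected error.** It assumes independence and eight true nulls. Weight and BMI are nearly the same measure, and the Background cites a 3.2 kg reduction on metformin in a placebo-controlled trial, so those two nulls may be false. Six remaining true nulls would give 26.5% under independence.
- **That the sponsor means to choose a list after seeing results.** The ambiguity permits this; nothing shows intent.
- **That the second list means unadjusted BMI and HbA1c values.** It gives no form. Shorthand for change is at least as plausible.
- **That the AFSS cannot serve two roles.** One instrument can inform a binary primary and also be reported as a burden score. The fault is narrower: conflicting roles, no combining rule, and no blinding described.

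The plan also promises public registration. A registered list might settle the matter, but it is not part of these documents and the plan does not name it as governing.

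**Conclusion.** The point holds as a modest inconsistency that is cheap to repair. Five of eight distinct secondary outcomes appear in only one of two current lists, and no section says which governs. The AFSS is secondary in one section and helps determine the sinus-rhythm primary in the other, with no combining rule. These findings need no assumption beyond the text.

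The multiplicity finding is separate. With all nulls true and one test per outcome, the chance of at least one false-positive secondary is 22.6%, 26.5% or 33.7% under independence (five, six or eight outcomes), and about 16% to 30% for all eight at assumed common correlations of 0.8 to 0.3. The exact figure depends on correlations the documents do not give, but every value in that range is well above 5%.

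**What to change.** Three edits:

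1. Put one identical secondary list in Trial Objective and Purpose and in Outcomes and Assessment of Efficacy, each item at 6 months: weight change, BMI change, HbA1c change, AFSS burden, arrhythmia- or drug-related hospitalization, antiarrhythmic drug count, repeat ablations and thromboembolic events.
2. Delete the AFSS from the primary-outcome sentence in Outcomes and Assessment of Efficacy. Word the primary as sinus rhythm at 6 months by EKG and chart review, which matches the six-month endpoint in Trial Objective and Purpose. The AFSS is then secondary only.
3. State in the Statistics section that, among efficacy outcomes, only the primary is tested for a confirmatory claim at P < .05. Secondary efficacy results are given as estimates with 95% confidence intervals and called exploratory.

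The third edit must be confined to efficacy. A blanket limit of P < .05 to the primary would remove the only stated threshold for the two-monthly analyses in Assessment of Safety, which turn on statistical significance. Leave those analyses outside the new wording, and state that thromboembolic events are also reviewed there as adverse events.

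The cost is wording in three sections and no added patients. The downside is that no secondary result can be claimed as confirmatory. If the sponsor wants such claims, the alternative is a stated procedure, such as a fixed testing order, Holm, or Bonferroni at 0.05 / 8 = 0.00625 per test.

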## **Background:**

Atrial fibrillation (AF) is the most common arrhythmia and its prevalence is projected to rise with the increase in age and comorbid disease in the patient population. AF is associated with significant morbidity and a nearly doubled risk of death.

As such the development of therapies which prevent or slow the progression of AF is imperative. In randomized controlled trials of therapies for AF, pharmacologic maintenance of sinus rhythm has not been demonstrated to be superior to therapies to control ventricular rates. In addition, medical therapy to maintain sinus rhythm was associated with significant cost and increased rates of hospitalization . However, in an "on treatment" analysis of the AFFIRM study which originally compared rhythm and rate control strategies, at an average of 3.3 years of follow up, the presence of sinus rhythm was associated with a significantly decreased risk of death (hazard ratio = 0.53). These findings suggest that the adverse effects of antiarrhythmic drugs in rate versus rhythm control studies offset the benefits of maintaining sinus rhythm when they are successful. Catheter ablation of the pulmonary veins and atria has been demonstrated to decrease the frequency of AF by 70-80% in several studies and provides a promising alternative to antiarrhythmic therapies.

Obesity is a known risk factor for AF and weight reduction through caloric reduction and exercise has been demonstrated to decrease the duration and symptomatic burden of AF in overweight and obese individuals in a randomized controlled trial. In a recently published retrospective cohort study of a physician led weight management intervention, successful reduction of 10% of body weight was associated with a six-fold increase in arrhythmia free survival. Similarly, in a cohort study of overweight and obese patients undergoing catheter ablation for AF, a program of aggressive risk factor management prior to ablation led to improved glycemic control, blood pressure reduction, favorable left atrial remodeling and a nearly fivefold increase in AF free survival at two years with less use of antiarrhythmic medications.

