Metformin hydrochloride (hereafter referred to as metformin) is the first-line pharmacologic therapy of Type II diabetes and has been associated with modest but sustained weight loss in diabetic individuals . There has not been a randomized controlled trial to assess the weight effect of metformin on non-diabetic individuals who are overweight or obese. However in retrospective studies of metformin use in overweight and obese euglycemic individuals, metformin has been associated with modest weight loss (2.99.0 kg) without evidence of hypoglycemia.  In a placebo controlled randomized controlled trial of metformin therapy of nondiabetic individuals with coronary disease and a large waist circumference, metformin use was associated with a 3.2 kg reduction at 18 months but did not improve other surrogate markers of cardiovascular disease. The known gastrointestinal side effects of metformin therapy occurred with the expected frequency in these studies.

In addition to obesity, there is significant epidemiologic and molecular data which implicates inflammatory, metabolic, and oxidative stress in the development and maintenance of AF. C-Reactive Protein (CRP) levels are known to be elevated in patients with AF and increasing CRP has been demonstrated to correlate with increasing AF burden. Development of AF was associated with a shift from glycolytic to ketolytic metabolism.  In genome wide transcriptional studies, patients susceptible to AF demonstrated decreased expression of sets of genes related to metabolic and oxidative stress responses. 

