Metformin acts by decreasing hepatic glucose production and increasing skeletal muscle uptake of blood glucose. These effects are thought to be in part mediated by metformin induced activity of AMP-activated protein kinase (AMPK) alterations in atrial calcium channels. In canine models of atrial fibrillation AMPK activation limits AF promoting In murine models of atrial fibrillation in which liver kinase B1, an activator of AMPK, is deleted, AF develops spontaneously in an age dependent manner and progresses from a paroxysmal to a persistent form in a similar manner to that seen in AF patients. Mutations in PRKAG2 gene, part of a subunit of AMPK have also been associated with early onset AF, and familial conduction diseases including Wolff-Parkinson-White syndromes. In transcriptional studies of human atrial fibrillation, AMPK subunit expression is increased in patients susceptible to AF but who remain in sinus rhythm while AMPK subunit expression is decreased in patients persistently in AF. This further suggests AMPK activity is protective in human AF.

Given the benefits of weight loss in AF, the benefit of metformin for weight loss, and the experimental and genetic evidence linking AMPK activation to metformin therapy and reduction in AF risk, the potential of metformin as an upstream therapy is promising.

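### The pre-specified comparison of 5% weight losers on metformin with 5% weight losers in the control group selects both arms on a post-randomisation variable that metformin is expected to change, so it does not estimate a treatment effect

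*Combined protocol and SAP*

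**What the plan says.** The section Outcomes and Assessment of Efficacy first sets the main analysis: "The primary outcome by intention to treat analysis will be maintenance of sinus rhythm". It then introduces further analyses with "Pre-specified subgroup comparisons will include", and the first of these is "comparing patients randomized to metformin who have a 5% reduction in weight at 6 months to all control patients who achieve a 5% reduction". The same sentence adds a second comparison, of the metformin losers with all controls. It does not name the outcome to be compared; I take it to be the rhythm outcome. It gives the 6-month time point only for the metformin group.

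Four other statements bear on this:

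- Weight is an outcome of the trial. Trial Objective and Purpose says: "Secondary endpoints are amount of weight loss, change in BMI".
- The protocol expects metformin to change weight. Background cites a placebo-controlled trial in which "metformin use was associated with a 3.2 kg reduction at 18 months", and its closing rationale begins "Given the benefits of weight loss in AF, the benefit of metformin for weight loss".
- Controls can also lose weight. Trial Design says: "All patients will receive information on dietary changes to promote weight loss and will be encouraged to increase exercise activities".
- The Statistics section gives a chi-square test, analysis of variance and a two-sided 5% level for every test. It sets no separate rule, adjustment or caution for the weight-loss comparison.

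**The concern.** Filtering both arms by the same 5% rule looks even-handed, but randomisation balances the arms as a whole, not the parts of them that later lose weight. A control patient who reaches 5% did so without the drug. The metformin patients who reach 5% include such people and also people who got there only because of the drug. If those two kinds of patient have different underlying AF risk, the groups differ even when metformin does nothing to AF.

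The filter also largely holds fixed a route by which the protocol expects metformin to work. Part of any real benefit could be that more metformin patients become weight losers, and comparing losers with losers discards that part.

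Timing adds a smaller problem. Weight at 6 months is read at the same visit as the final rhythm assessment, so weight loss need not precede recurrence.

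At stake is interpretation. A result carrying the pre-specified label and tested at 5% could be read as the effect of metformin in patients who lose weight, and could disagree with the primary result for structural reasons alone.

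**Working it through.** **Inputs from the Statistics section.** Control recurrence 30%; a reduction of 30%, read as relative; 400 per arm; up to 3% attrition; 80% power; two-sided 5%. All weight-loss shares and prognosis figures below are assumptions.

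**The plan's own figure.** 30% v 0.70 × 30% = 21%, with continuity correction, needs 389 per arm. 389/0.97 = 401.03, rounded up to 402, against the stated 400, so the primary sample size reproduces. No figure is given for the weight-loss comparison. Evaluable patients: 400 × 0.97 = 388 per arm.

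**Step 1. No effect of metformin or weight on AF.** Let p be the share who lose 5% without the drug, with recurrence a. Everyone else has recurrence b, where pa + (1 − p)b = 30%. Metformin adds a share q of losers drawn from everyone else and stops nobody from losing weight.

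- Control losers recur at a.
- Metformin losers recur at (pa + qb)/(p + q).
- False difference = [q/(p + q)] × (b − a).

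The difference is zero if metformin moves nobody across 5% (q = 0) or if prognosis is equal (a = b). Its sign is the sign of b − a. With p = 10%:

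| a | b | q | Metformin losers | Control losers | Difference (points) |
|---|---|---|---|---|---|
| 20% | 31.1% | 15% | 26.7% | 20.0% | +6.7 |
| 20% | 31.1% | 5% | 23.7% | 20.0% | +3.7 |
| 20% | 31.1% | 25% | 27.9% | 20.0% | +7.9 |
| 25% | 30.6% | 15% | 28.3% | 25.0% | +3.3 |
| 15% | 31.7% | 15% | 25.0% | 15.0% | +10.0 |
| 40% | 28.9% | 15% | 33.3% | 40.0% | −6.7 |

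First row in full: b = (0.30 − 0.10 × 0.20)/0.90 = 0.311; (0.10 × 0.20 + 0.15 × 0.311)/0.25 = 0.267.

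**Step 2. The same question with a continuous weight model.** Percent weight loss = 1 + s (metformin only) + 5 × [rU + √(1 − r²) × noise], where U is an unmeasured patient factor. Logit of recurrence = b0 − gU, with overall recurrence fixed at 30% in both arms. The pairs (r, g) were (0.5, 0.5), (0.5, 1) and (0.7, 1); a reversed case used (−0.5, 0.5).

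| s | Losers, control v metformin | False difference (points) | Reversed case |
|---|---|---|---|
| 0 | 21% v 21% | 0 | 0 |
| 2 | 21% v 35% | +1.3 to +2.7 | −1.6 |
| 3.2 | 21% v 44% | +2.1 to +4.3 | −2.5 |
| 4 | 21% v 50% | +2.6 to +5.4 | −3.1 |

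Here s is in percent of body weight. The 3.2 kg in Background would be 2% at 160 kg, 3.2% at 100 kg and 4% at 80 kg, but it was observed at 18 months, not 6.

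**Step 3. Benefit acting only through weight.** Suppose 5% loss itself lowers recurrence from 32% to 12%, and 10% of controls and 25% of metformin patients reach it.

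- Control overall: 0.10 × 0.12 + 0.90 × 0.32 = 30%.
- Metformin overall: 0.25 × 0.12 + 0.75 × 0.32 = 27%.
- Losers: 12% v 12%.

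The 3-point benefit shows as 0, and no prognostic difference is needed. In the Step 2 model with s = 3.2, no shared cause and an assumed odds ratio of 1/6 for weight loss, overall recurrence is 30.0% v 23.9% but losers are 8.5% v 8.5%. With a shared cause (r = 0.7, g = 1) and an odds ratio of 1/2, overall is 30.0% v 27.8% in favour of metformin, while losers are 8.7% in control v 11.7% on metformin.

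**Step 4. Precision.** In the first row of Step 1 the groups are 0.25 × 388 = 97 and 0.10 × 388 ≈ 39. SE = √(0.267 × 0.733/97 + 0.20 × 0.80/39) = 0.078, so the 95% interval is about ±15 points. A false 6.7 points would reach P < .05 about 14% of the time, against 5% nominal. In Step 2 at s = 4, with positive r, that chance is 7.5% to 20.7%.

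**The case against.** The best defence is that comparing losers with losers asks whether metformin does anything beyond weight. Background gives AMPK activation as a second route, and if the whole benefit runs through weight then 0 is the right answer to that question, while the intention-to-treat analysis still reports the total. This stands in part, but only if nothing else drives both weight loss and recurrence. The plan neither states that question nor adjusts for anything.

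Other limits stand in full:

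- A reader might infer that the bias runs mainly against metformin. The documents do not support that. They give no recurrence rate for people who lose weight unaided, and the sign reverses if those people have worse prognosis.
- A reader might take the prognostic difference as established from the cohort in Background, where "successful reduction of 10% of body weight was associated with a six-fold increase in arrhythmia free survival". That is a retrospective association for a different threshold and cannot separate prognosis from effect.
- The false-significance rates in Step 4 are modest, and the protocol presents this only as a subgroup comparison.

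**Conclusion.** The concern holds. Followed as written, the comparison is not randomised, does not estimate a treatment effect, and largely removes benefit that acts through weight. That last failure follows from the protocol's own rationale.

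A false difference needs two further conditions: metformin must move patients across the 5% line, and unaided weight loss must be related to prognosis. Under plausible assumed inputs it is about 1 to 7 points against metformin. Stronger inputs give up to 10 points, and opposite prognosis gives a false benefit (−1.6 to −3.1 points in the weight model, −6.7 in the simple one). No single figure should be quoted as the expected bias, because the documents give no 6-month weight distribution.

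A reader might also infer that the trial's main conclusion is compromised. It is not: the primary analysis compares the arms as randomised. This should be corrected to protect the interpretation of a secondary result.

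**What to change.** Remove the comparison from the pre-specified subgroup list, or keep it labelled exploratory and non-causal, reported without a P < .05 claim. Edit the comparison with all controls in the same sentence at the same time, since it also selects on weight after randomisation.

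In its place, in all randomised patients:

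1. For effect modification, test a treatment-by-baseline-BMI interaction. This answers a different question from the responder contrast, but uses a variable fixed before treatment.
2. For the weight question, specify an exploratory mediation analysis with weight change measured before the outcome window. Weight at the ablation visit qualifies, though it reflects only six weeks of treatment. Weight at 3 months qualifies only for recurrence after month 3, because rhythm is also assessed at 3 months. Adjust for baseline weight, AF type and other collected baseline prognostic factors, state the assumptions, and report the result as non-randomised evidence.

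The cost is protocol wording and a little more analysis; baseline BMI and the serial weights are already collected. The sponsor loses a simple responder contrast, and the mediation analysis remains open to unmeasured confounding.
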